9.7.1 Objectives, endpoints, analysis, and sample size justification

The primary objective of Phase 0 dose escalation and expansion studies is to determine the MTD and to identify patients with positive PK and PD effects and the key secondary objective is to explore the clinical effect of everolimus plus ribociclib in recurrent GBM patients. The exploratory objectives are to explore pharmacometabolomics (PM) markers, mechanisms of resistance, and to examine evidence for CDK4/6 and mTOR pathway activity described in the

previous section. The primary endpoints are MTD as well as PK and PD effects, which are for the Phase 0 component, and the progression-free survival (PFS) is a key secondary endpoint, which are for the Phase 2 dose expansion component. Other endpoints for the secondary objective are RP2D, overall survival (OS) and drug-related toxicity. In particular, the positive PK effect will be defined as unbound ribociclib and everolimus drug concentrations in non-enhancing tumor tissue $>$ *in vitro* IC50 of each agent. The positive PD effect will be defined as $>30\%$ decrease in pRB-positive cells and $>30\%$ decrease in pS6-positive cells. The PFS will be defined as the time duration from the date of surgery to disease progression or death from any cause and the OS the time duration from date of surgery to death from any cause. A Kaplan-Meier (KM) curve will be used to summarize the distributions of survival outcomes (PFS and OS) and the median PFS/OS and their associated 95% confidence interval (CI) will be estimated using KM estimates.

This study will be prospectively conducted as an open-label, multi-institution study (up to 3 sites) with four dose escalation and three time-escalation cohorts in the Phase 0 component and exploratory efficacy study in the dose expansion component. Patient assigned to one of the four dose escalation levels in Phase 0 will be assigned to one of three time-escalation cohorts in turn with 1 patient being placed into cohort 1, then 1 patient into cohort 2, and then 1 patient into cohort 3 and so on. Approximately 8 subjects in each cohort will be enrolled.

The required sample size will be from 6 (when Level 0 becomes MTD) to 32 patients (if dose Levels 1-5 are expanded to 6 and the time cohort is expanded to 8 additional patients). The expected sample size for the Phase 2 dose expansion study will be at most 3 to 12 patients under the assumption that at most 50% of Phase 0 dose escalation patients will have PK/PD responses. Considering the drop-out rate of 20%, the total required sample size will be approximately 30 patients.

Table 15 Target Accrual

Phase 0 Study	Cohort 1 Target Accrual	Cohort 2 Target Accrual	Cohort 3 Target Accrual
High-grade Glioma	3-11	3-20	3-11

The Phase 2 dose expansion study will be considered an exploratory study and no formal statistical comparison will be carried out. Thus, in this case, its outcome will be summarized with descriptive statistics (N, median, mean, standard deviation, minimum, maximum, and the 80% confidence interval [CI] for the mean).

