4.1.2 Phase 2 Dose expansion

Patients with tumors demonstrating favorable PK and PD will proceed to Phase 2 Dose Expansion. In Dose Levels 1-3, patients will continue treatment with the same treatment level as given in Phase 0, patients should take the treatment continuously in 28d cycles with 3 weeks on / 1 week off after surgery. In Dose Level 4+, patients should take everolimus in one dose weekly; ribociclib will be taken for 21 consecutive days followed by 1 rest week. The dose will be per Table 7. If more than one DLT is observed in 6 patients in the Phase 2 dose expansion, the enrollment will be stopped and the previous lower dose level will be considered the RP2D and will be given for the remaining patients enrolled. If more than one DLT is occurred with the Level 0, the study will be stopped due to toxicity. Typically DLTs are defined by 1 cycle of treatment, which is 28 days. Since Phase 0 treatment is given for only 5 days, Phase 0 dose escalation will only be determined by Phase 0 DLT rules unless determined otherwise by the DSMB. Patients will be treated until unacceptable toxicity is observed, or until disease progression as assessed by radiographic or clinical metrics. Preliminary rates of progression-free survival in patients with high-grade gliomas treated with ribociclib+everolimus will be measured through radiographic and clinical response metrics, specifically Response Assessment in Neuro-Oncology (RANO) criteria and investigator discretion. Phase 2 participants will return to the clinic to monitor safety per the schedule of events until treatment is ended and will then be contacted approximately every 3 months by letter or phone for collection of survival data. The start of follow up for long-term survival begins following completion of the Day 30 safety follow up call.. All Phase 0/2 participants will be followed for survival for up to 5 years.

Common Toxicity Criteria Adverse Event (CTC AE 4.03) will be utilized to review ribociclib+everolimus treatment effects in patients with brain tumors.

Trough steady-state blood samples will be obtained on days 1, 8, 15, and 22 of cycles 1 and 2 prior to the administration of ribociclib+everolimus on that day. Note: ribociclib+everolimus will be administered in the clinics on the clinic visit days to ensure the collection of trough level samples.

PHASE 2 STUDY				
	Cycle 1 (28 d)	Cycle 2 (28d)	Subsequent cycles (28d)	End of study
Day of cycle	D1, D8, D15, D22	D1, D8, D15, D22	N/A	N/A

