6.1.5 Guidelines for continuation of treatment beyond tumor resection (Optional Phase 2)

Patients with positive PK and PD responses will be provided the option of continuing on therapy until tumor progression. PK data evaluates the drug concentration in enhancing and non-enhancing region of the tumor. PD analysis evaluates the biomarker response after 5-day treatment and compares this with archival tissue. If both are positive the patients will be enrolled into Phase 2 portion of the trial with the same dose level taken during Phase 0 (unless there is more than one DLT observed in Phase 2, see Section 4.1.2). If the PD data is not conclusive due to treatment effect or limited tissue samples from the surgery, the PK data would be the primary guidance on deciding phase 2 enrollment.

Some anticipated risks and safety considerations of the ribociclib+everolimus combination will be closely monitored. Preclinical and Phase I clinical data available from ongoing studies with ribociclib and everolimus separately suggest few overlapping toxicities for the proposed

Initial Version date: 10/16/2018

Revision date: 03/11/2019, 5/07/2019, 09/26/2019, 03/17/2020, 08/26/2024

combinations. Special attention will be paid to blood counts (cytopenias), mucositis, liver function test abnormalities and QTc prolongation. Clinical data from the [CLEE011X2101] study do not show marked accumulation in ribociclib with time, suggesting that it does not substantially inhibit its own metabolism or clearance. Everolimus and ribociclib are *in vitro* inhibitors and substrates of CYP3A4, and the latter is also a time-dependent CYP3A4 inactivator. The available preclinical and clinical data therefore suggest the possibility of a drug interaction, specifically one that may increase exposure to everolimus. Based on simulation using Simcyp software (Simcyp Version 12, release 1), the projected increase in the AUC_{0-6h} of everolimus was 3.5-fold following the starting daily dose of 200 mg ribociclib co-administered with 2.5 mg of everolimus for 14 days. No significant effect on ribociclib metabolism was predicted when co-administered with everolimus. Appropriate eligibility criteria, dose modification guidelines and stopping rules are included in this protocol.

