7.1.1.11.1 Day 1 Enrollment

The following assessments will be performed on Day 1:

- Review of surgical and medical procedures
- ECOG
- 12-lead ECG
- Collection of AEs and Concomitant medication(s)
- Screening assessments not previously collected as noted in section [7.1.1.9](#)
- Day 1 pre-dose PK sample
- Day 1 pre-dose biomarker blood sample
- Confirm eligibility prior to study drug administration
- In clinic/hospital study drug administration
- Provide the patient the following for home dosing on Days 2 and 3
 - Instructions for study medication
 - Dosing Diary
 - Symptom Diary
 - Study drug

7.1.1.11.2 Day 2 and 3

Phase 0 patients will record study drug administration in the Dosing Diary and record symptoms in the Symptom Diary.

7.1.1.11.3 Day 4

The following assessments will be performed on Day 4:

- Review of medical and surgical procedures
- Collection of AEs and Concomitant medication(s)
- Review of home dosing diary and symptom diary

- 12-lead ECG
- Trough PK Sample (Dose Levels 0-3)
- Laboratory testing (may also be performed as a pre-surgical assessment on Day 5 or Day 6):
 - Chemistry, (comprehensive metabolic panel, magnesium, phosphorus)
 - Hematology (CBC w/differential)
 - Coagulation (PT/INR, aPTT)
 - eGFR
- In clinic/hospital study drug administration
- PK blood sampling: 0.5, 1, 2, 4, 7 hours post-dose (Dose Levels 0-3)
 - *In Dose Level 4+ only, PK blood sampling will occur on Day 5 instead of Day 4.*

7.1.1.11.4 **Day 5**

- Review of medical and surgical procedures
- Collection of AEs and Concomitant medication(s)
- 12-Lead ECG (if not collected on Day 4)
- In clinic/hospital study drug administration
- Craniotomy (Day 5 for Cohort 1 & 2; Day 6 for Cohort 3)
 - PK Collection of blood, CSF and tumor
 - Biomarker tumor collection
- Dose Level 1-3: Day 5 trough/24hrs post-dose
- Dose Level 4+ only: PK blood sampling: pre, 0.5, 1, 2, 4, 6, 8 and 24 hours (Day 6) post-dose

7.1.1.11.5 **Follow-up / EOT visit**

Phase 0 patients will have a follow up visit 7-14 days after surgery (routine post-operative visit). All Phase 2 patients should be scheduled for an EOT visit within 7 (± 3) days following discontinuation of study treatment.

The following assessments will be performed at the EOT visit:

- Physical exam
- ECOG performance status
- Weight
- Vital signs
- Laboratory blood collections
 - CMP, magnesium, phosphorus
 - Hematology (CBC w/differential)
 - Urine pregnancy test (if applicable)
- 12-lead ECG

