9.6 Secondary and exploratory objectives

	Objective	Endpoint
Secondary	
 • To explore safety and efficacy in recurrent high-grade glioma patients with demonstrated PK and PD effects and determine RP2D • To describe PK for Phase 2 patients 	
 • Progression-free survival (PFS): rate measured from time of surgery to date of recurrence • Overall survival (OS): Median Overall Survival (OS) from time of surgery to date of death from any cause • Drug-related toxicity • RP2D • Systemic PK profiles of ribociclib and everolimus when combined.
Exploratory	
 • To explore evidence for CDK4/6 and mTOR pathway activity in tumor tissue (as compared to archival tissue) and mechanisms of resistance • Pharmacometabolomics: To explore the plasma metabolomic signature of the exposure of ribociclib and everolimus 	
 • Quantification of total and phosphorylated forms of Rb, FoxM1, S6, 4EBP, as well as cleaved Caspase-3 and MIB1. Expression of Cyclin D1, Cyclin E1, PI3K/mTOR signaling components • Plasma metabolomic profiles (i.e., levels of ~250 metabolites) at the pretreatment and at predefined time points after the combination therapy. • Pharmacogenomics studies using RNA-seq and Whole Exome Sequencing to identify alterations in gene expression and mutational profile between pre-

	
• To identify resistance mechanism and alternate pathways	treatment and post-treatment tissues and plasma.
--	---	--

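### Phase 2 PFS is timed from surgery, but patients join Phase 2 only after their tumour PK/PD is read, so the median PFS among entrants is biased upward

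*Combined protocol and SAP*

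**What the plan says.** **Time origin.** Section 9.7.1 gives "The PFS will be defined as the time duration from the date of surgery to disease progression or death from any cause". Its definition for overall survival uses the same origin: "the OS the time duration from date of surgery to death from any cause". Section 9.6 also times PFS from surgery, as a "rate measured from time of surgery to date of recurrence". Section 7.1.1.8.3 uses the same origin. The last two leave death out of the PFS event, unlike 9.7.1.

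**Population.** Section 9.7.1 says that "the progression-free survival (PFS) is a key secondary endpoint, which are for the Phase 2 dose expansion component". OS appears there only among the other endpoints for the secondary objective. Section 9.3.1 is headed Full Analysis Set but defines no set.

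**Entry to Phase 2.** Section 4.1.2: "Patients with tumors demonstrating favorable PK and PD will proceed to Phase 2 Dose Expansion". Section 6.1.5, after describing the tumour PK and PD readings: "If both are positive the patients will be enrolled into Phase 2 portion of the trial". Entry is optional for the patient, and treatment runs until progression.

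**The gap.** The dated post-operative milestone before Phase 2 is in 7.1.1.11.5: "Phase 0 patients will have a follow up visit 7-14 days after surgery". No maximum interval from surgery to Cycle 1 Day 1 is given.

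**Estimator.** Section 9.7.1 plans Kaplan-Meier medians with 95% confidence intervals. It mentions no delayed entry and no landmark.

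**The concern.** The clock starts at craniotomy, but membership of the analysed group is settled later. Before entry, the tissue has to be assayed by LC-MS/MS (7.1.1.1), checked for viable tumour (7.1.1.7.2) and compared with archival tissue by immunohistochemistry (7.1.1.3). Someone who dies in that interval never becomes a Phase 2 patient. Someone who worsens so clearly that Phase 2 is not started leaves no event in the curve either. Each entrant, meanwhile, is counted as at risk from surgery, over a period in which they could not have died. This is immortal time, or left truncation that the analysis does not account for.

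PFS is the key secondary endpoint, and exploring efficacy is a stated objective. In a single arm the median is the efficacy result. A slower laboratory turnaround would lengthen it without any change in the drug's effect.

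**Working it through.** **The plan's own figure.** The documents give no PFS or OS median, event count or power for Phase 2. The one related figure is the expected Phase 2 size of 3 to 12 (9.7.1). It reproduces as 50% of 6 = 3 and 50% of 24 (three time cohorts of 8) = 12.

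**Assumed inputs, because the documents give none.** Gap g of 2 to 8 weeks, with 4 weeks = 28/30.44 = 0.92 months. True median PFS from surgery m of 2 to 4 months, and true median OS of 6 to 12 months. Every event in the gap is taken to prevent entry.

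**Formulae.** For a Weibull time from surgery with shape k and median m, the median from surgery among patients event-free at g is (m^k + g^k)^(1/k). The share with an event before g is 1 − 2^(−(g/m)^k). With k = 1 (constant hazard) these become m + g and 1 − 2^(−g/m).

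**Constant hazard, m = 3 months.**

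| Gap | Median from surgery among entrants | Increase | Share with event in gap |
|---|---|---|---|
| 2 weeks (0.46 months) | 3.46 months | 15% | 10% |
| 4 weeks (0.92) | 3.92 | 31% | 19% |
| 6 weeks (1.38) | 4.38 | 46% | 27% |
| 8 weeks (1.84) | 4.84 | 61% | 35% |

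Over m = 2 to 4 months and gaps of 2 to 8 weeks, the increase runs from 0.46/4 = 12% to 1.84/2 = 92%.

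**Hazard shape, m = 3 months, g = 4 weeks.** k = 2: (9 + 0.85)^(1/2) = 3.1 months. k = 1.5: 3.3. k = 1: 3.9. k = 0.7: 5.0. The bias is always upward, and small when early hazard is low.

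**OS, only if restricted to Phase 2 entrants.** m = 9 months, g = 4 weeks, constant hazard: 9 + 0.92 = 9.9 months, or +10%.

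**Precision.** With n = 12 and no censoring, the 3rd and 10th ordered times give a 96% interval for the median. With a 3-month median this typically runs from about 1.1 to 6.6 months, so the shift is smaller than the sampling error.

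**Does each remedy work?** Simulation, constant hazard, m = 3 months:
- Timed from Cycle 1 Day 1, the median is 3.0 months.
- Delayed-entry Kaplan-Meier from surgery, with gaps spread evenly over 2 to 6 weeks, gives about 3.4 to 3.5 months, against 3.9 without it. Nobody is at risk before the shortest gap, so the curve is conditional on being event-free to that point: 3 + 0.46 = 3.46. If every gap were 4 weeks it would give 3.9, no better than the ordinary estimate.

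**A separate exclusion.** Section 7.1.1.8 treats patients who progress before the end of Cycle 1 as not evaluable. If PFS were also limited to evaluable patients, the 3-month, 4-week case becomes 3 + 0.92 + 0.92 = 4.8 months from surgery and still 3.9 from Cycle 1 Day 1.

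**The case against.** **OS.** A reader might infer that both medians are inflated. The documents do not support that. OS is not tied to Phase 2, its analysis set is undefined, and all Phase 0 patients are followed for survival for up to 5 years (4.1.1, 4.1.2). On all Phase 0 patients, surgery is a valid origin. It is also valid for all PK/PD-positive patients whether or not they start Phase 2, since positivity comes from tissue taken at surgery. This objection stands.

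**Progression.** A reader might also infer that the whole gap is progression-free by selection, so that 10% to 35% of qualifying patients drop out of the curve. No section requires freedom from progression at Cycle 1 Day 1. It is implied by treatment running only until progression (6.1.5), and progression is a permitted ground for withdrawal (7.1.1.13). The imaging minimum is every 3 months (7.1), so silent growth in the gap could surface at a later scan and count as an event. Those percentages are therefore nearer an upper figure, for continuous detection and constant hazard. This also stands, but it does not touch deaths or clinically evident progression that prevents entry.

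**Exploratory and small.** Section 9.7.1 plans no formal comparison, and no PFS benchmark is given. So no error rate is affected, and the documents do not show that the median will be set against particular outside figures. But the bias is systematic: more patients would not remove it.

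**Surgery as origin.** Surgery is a reasonable time zero, and study drug starts before it. The fault lies in pairing that origin with a group chosen afterwards.

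**Conclusion.** The concern holds for PFS. As written, the plan yields a Kaplan-Meier median from surgery on patients who had to survive to a later decision, with nothing to correct for it. The direction is upward. The size is unknown. For a 4-week gap and a true median of 3 months, both assumed, it is about 0.9 months under a constant hazard, with readings of 3.1 to 5.0 months under Weibull shapes 2 to 0.7. It is smaller where progression in the gap is picked up only at a later scan. For OS the point is conditional: it applies only if OS is estimated on Phase 2 entrants. The plan should be changed because PFS is its key secondary estimate and the change is one of definition.

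**What to change.** In 7.1.1.8.3, 9.6 and 9.7.1:

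1. Estimate Phase 2 PFS, and OS if it is reported on Phase 2 entrants, from Cycle 1 Day 1. Alternatively, keep surgery as origin and let patients join the risk set at Cycle 1 Day 1 (delayed-entry Kaplan-Meier), stating that the curve is conditional on being event-free at the shortest observed gap.
2. Report surgery-based OS on all Phase 0 patients, or on all PK/PD-positive patients whether or not they start Phase 2, and define that set in 9.3.1.
3. Report the surgery-to-Cycle-1 interval and the number of PK/PD-positive patients who did not start Phase 2, with reasons.
4. Use one PFS event definition; death is included in 9.7.1 but not in 7.1.1.8.3 or 9.6.

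**Cost.** Wording only: the dates are already collected, and survival follow-up of non-entrants is already planned.

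**Downsides.** Medians from Cycle 1 Day 1 will be shorter and less comparable with series timed from resection. They describe remaining time after entry, which equals the median from surgery only under a constant hazard. That clock also starts after the post-operative MRI that serves as the Phase 2 baseline. With 3 to 12 patients, delayed-entry estimates can be unstable early, and they help little if the gaps are similar. Neither option cures the exclusion in 7.1.1.8 of patients who progress before the end of Cycle 1, which needs its own correction.

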4.1 Description of protocol design

4.1.1 Phase 0

In the proposed trial, patients will be administered ribociclib+everolimus prior to surgical resection of their tumor. Recurrent GBM patients will be randomized into one of the three time-interval cohorts for the first two dose levels.

In the lead-in dose escalation study, the first six subjects (lead-in) will receive ribociclib 400 mg and everolimus 2.5 mg orally-administered in 5 daily doses with the last dose. If one or less patient experiences DLT among the 6 patients, this regimen with ribociclib 400 mg and everolimus 2.5mg will be considered safe and we will continue with the dose escalation phase of the study up to Level 6.

Four dose escalation levels:

Level 0: ribociclib 400mg and everolimus 2.5

Level 1: ribociclib 600mg and everolimus 2.5mg

Level 2: ribociclib 600mg and everolimus 5mg

Level 3: ribociclib 600mg and everolimus 10mg

Level 4: ribociclib 600mg daily for 5 days and everolimus 50mg given once on Day 5.

Level 5: ribociclib 600mg daily for 5 days and everolimus 60mg given once on Day 5.

Level 6: ribociclib 600mg daily for 5 days and everolimus 70mg given once on Day 5.

Three to fourteen (3-14) patients will be enrolled into each level to observe AEs and DLTs. Detailed DLTs definition will be summarized in [Table 9](#).

All patients will receive ribociclib and everolimus orally-administered in 5 daily doses.

Cohort 1: last ribociclib+everolimus dose 1 to 3 hours prior to craniotomy for tumor resection (n=8 patients)

Cohort 2: last ribociclib+everolimus dose 7 to 9 hours prior to craniotomy for tumor resection (n=8 patients)

Cohort 3: last ribociclib+everolimus dose 23 to 25 hours prior to craniotomy for tumor resection (n=8 patients)

In Dose Level 0 three to six patients will be enrolled into the time interval cohorts, sequentially whenever possible (e.g. cohort 1, cohort 2, cohort 3, cohort 1...), with at least 1 patient in each of the time intervals.

In Dose Level 1

Three to six patients will be enrolled into the time interval cohorts, sequentially whenever possible (e.g. cohort 1, cohort 2, cohort 3, cohort 1...), with at least one patient in time cohort 1 and two patients in cohort 2. If there are positive PK/PD results at the Maximum Tolerated Dose (MTD) or Optimal Biological Dose (OBD) dose level, the dose level will be expanded to 8 additional patients with 4 patients in each time cohort 1 and 3 (Sections [6.1.2](#) and [6.1.2.1](#)).

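### Section 9.7.1 misstates the Phase 0 sample size: its upper scenario as worded gives 44, not 32, and the DLT-free path to an expanded Level 6 needs 35

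*Combined protocol and SAP*

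**What the plan says.** Section 9.6.1 states that there will be no separate SAP, so Section 9.7.1 is the plan's only sample-size statement. It reads: "The required sample size will be from 6 (when Level 0 becomes MTD) to 32 patients (if dose Levels 1-5 are expanded to 6". Its parenthesis also adds 8 patients for the time-cohort expansion. It then says: "Considering the drop-out rate of 20%, the total required sample size will be approximately 30 patients". For the second component, the "expected sample size for the Phase 2 dose expansion study will be at most 3 to 12 patients", on the assumption that at most half of the Phase 0 dose-escalation patients respond. The design is described as having "four dose escalation and three time-escalation cohorts in the Phase 0 component", and "Approximately 8 subjects in each cohort will be enrolled". The table headed "Table 15 Target Accrual" gives 3–11, 3–20 and 3–11 for time cohorts 1, 2 and 3.

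The rules that generate the numbers are elsewhere. Section 4.1.1 lists Levels 0 to 6 and says that, if Level 0 is safe, "we will continue with the dose escalation phase of the study up to Level 6". Table 7 gives a minimum of 6 patients at Level 0 and 3 at each later level. Table 8 and the text below it in Section 6.1.2 take 3 patients per level, or 6 after one DLT, and require at least 6 treated to declare an MTD. Section 6.1.2.1 adds 8 patients after fewer than 2 DLTs in 6, and Section 4.1.1 makes that expansion depend on positive PK/PD results. Section 4.1.2 says: "If more than one DLT is occurred with the Level 0, the study will be stopped due to toxicity".

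**The concern.** The stated range does not follow from the plan's own enrolment rules, and its figures do not agree with each other. A drop-out-adjusted total should not be smaller than the unadjusted maximum. A scenario described as five levels of six plus eight cannot come to 32. The IRB, the DSMB and the sponsor read this section for the planned number of exposed patients, and a trial that follows Table 8 with no toxicity at all could exceed it.

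**Working it through.** **Inputs.** Level 0 = 6 (Table 7; Section 4.1.1 table, 2+2+2). Later levels = 3, or 6 after one DLT (Table 8). The MTD level is brought to 6 (Section 6.1.2). Expansion = 8, at one level (Sections 4.1.1 and 6.1.2.1). Top level = 6. Drop-out = 20%.

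**Reproducing 32.**
- As worded, Levels 1–5 at six plus 8: 6 + 5×6 + 8 = 44. Without Level 0: 38. With only 3 at Level 0: 41.
- Read as escalation to Level 6 with three per level: 6 + 6×3 + 8 = 32.
- A four-level design (Levels 0–3): 6 + 3×6 + 8 = 32. That the figure was carried over from such a design is an inference.

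The second reading leaves Level 6 at 3 patients before expansion. The expansion follows 6 treated, and the Section 4.1.1 table lists the extra 3 separately from the 4+4.

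**DLT-free path through Level 6.** 6 + 5×3 + 6 = 27 without expansion; 27 + 8 = 35 with it.

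**Ceiling with one expansion.** 6 + 6×6 + 8 = 50. Under Table 8 its chance is below 0.1%.

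**Level 0 as MTD.** With 0–1 DLT in 6 at Level 0 the study escalates, so Level 1 must be treated and must fail. That takes 6 + 3 = 9 (at least 2 of 3 with DLT) or 6 + 6 = 12 (1 of 3, then at least 1 of 3), counting complete groups of three. Paths that go higher and step back down to Level 0 take more.

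**Drop-out.** 24/0.8 = 30, but 32/0.8 = 40, 35/0.8 = 43.75 → 44, and 50/0.8 = 62.5 → 63. So the figure of about 30 rests on 24.

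**Phase 2.** 32 − 8 = 24 dose-escalation patients, and 0.5×24 = 12, as stated. The seven-level rules allow 6 + 6×6 = 42 dose-escalation patients, and 0.5×42 = 21.

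**Time cohorts on the 35-patient path.** By the Section 4.1.1 table: cohort 1, 2+1+4 = 7; cohort 2, 2+2+4×3+6 = 22; cohort 3, 2+0+4 = 6. By rotation (Sections 6.4.2 and 9.7.1): 27/3 = 9 each, plus 4 in cohorts 1 and 3, giving 13/9/13. The first exceeds Table 15's 20 for cohort 2, and the second exceeds its 11 for cohorts 1 and 3. At the low end, a stop at Level 0 gives 2/2/2, and 9 patients by the Section 4.1.1 table give 3/4/2. Both fall below a stated minimum of 3.

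**Chance that Phase 0 exceeds 32.** Binomial DLTs on the Table 8 tree, with one constant DLT rate at all levels (assumed; the plan gives none):

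| DLT rate | Expansion at any MTD of Level 1 or above | Never expanded |
|---|---|---|
| 0% | 100% | 0% |
| 5% | 87% | 10% |
| 10% | 60% | 16% |
| 15% | 36% | 12% |
| 20% | 18% | 6% |

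**The case against.** The strongest defence is that nothing operational depends on this total. Enrolment follows Table 8, drop-outs may be replaced (Sections 4.4 and 7.1.1.14), and there is no power calculation. That stands, and it limits the point to planning and reporting. A reader might infer that the study is undersized for its objectives; the documents do not support that.

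Four further defences stand at least in part.

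- **Six is not impossible.** Section 6.1.2 defines the MTD by no more than 1 DLT once at least 6 are treated, and escalation needs DSMB authorisation. If authorisation were withheld after 0–1 DLT in 6, Level 0 would meet the definition with 6 patients. It would be too strong to say that 6 can never apply.
- **The Phase 2 maximum of 12 is not an arithmetic slip.** It is half of the 24 dose-escalation patients left when the 8 expansion patients are removed from 32. It is out of date only against the seven-level design.
- **Exceeding 32 is not a foregone conclusion.** The 8-patient expansion needs positive PK/PD. Section 2.3 reports persistent negative PK for everolimus when Levels 4–6 were added, in the same sentence that reports no dose-limiting adverse events. Without the expansion, the DLT-free total is 27, inside both 30 and 32.
- **Table 15's maxima sum to 42, which is not itself an error.** Cohort maxima need not occur together. Section 6.4.2 also allows flexible assignment, so the cohort splits above are nominal.

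Reading the phrase as escalation to Level 6 narrows the gap from 12 patients to 3 but does not close it.

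**Conclusion.** The Phase 0 size in Section 9.7.1 is wrong as written. Its own scenario gives 44, and the most favourable reading is still 3 short of the 35 needed on a DLT-free path to an expanded Level 6. On the ordinary Table 8 route the entry for Level 0 as MTD should be at least 9 (9 or 12 on the direct path). The total of about 30 contradicts the stated maximum before drop-out. The count of four dose levels contradicts the seven listed in Section 4.1.1, which itself introduces them as four.

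These counts assume that Table 8 governs the size of each level and that one level is expanded. Section 2.3 instead speaks of six patients at each level; if that governs, 50 becomes the DLT-free size with expansion. Under Table 8 a reader should not take 50 as the expected size. The chance of exceeding 32 runs from 18% to 100% if the expansion always occurs and from 0% to 16% if it never does, over assumed DLT rates of 0–20%. A correction is worth making because it is cheap and the section is the only statement of planned exposure.

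**What to change.** Amend text and tables only.

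1. Restate Phase 0 evaluable patients by scenario: 6 if the study stops at Level 0; at least 9 if Level 0 is the MTD after Level 1 fails (9 or 12 on the direct path); 27 DLT-free through Level 6 without expansion; 35 with it; and a very unlikely ceiling of 50 with one expansion.
2. Name the case to which the 20% drop-out applies and replace the total of about 30: 35 becomes 44, and 50 becomes 63.
3. Restate the Phase 2 maximum as 50% of a named dose-escalation base: 21 of 42 at the ceiling.
4. Replace the count of four dose levels with the seven listed.
5. Reconcile the per-level size (Section 2.3 against Table 8) and the time-cohort assignment (Section 4.1.1 table against Sections 6.4.2 and 9.7.1). Then recompute Table 15's minima and maxima, and the figure of about 8 per cohort, from the reconciled rules.

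The cost is an amendment and a higher accrual ceiling before the IRB and DSMB. At the 57–76 patients per year in Section 9.7.2, 44 enrolled takes 12×44/76 = 6.9 to 12×44/57 = 9.3 months. Sixty-three takes 9.9 to 13.3 months, so the 12-month accrual statement is at risk only at the ceiling and the slower rate.
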